2. INTRODUCTION

This open-label, global, nonrandomized multicohort trial is designed to provide a benchmark of efficacy for INCB086550 in key indications in which other PD-(L)1 inhibitors have already demonstrated efficacy.

2.1. Background

INCB086550 is a small molecule inhibitor of PD-L1 (also known as CD274). PD-1, also known as CD279, is a cell surface receptor expressed on activated T cells, natural killer T cells, B cells, and macrophages (Greenwald et al 2005, Okazaki and Honjo 2006). PD-1 functions as an intrinsic negative feedback system to prevent the activation of T cells, which in turn reduces autoimmunity and promotes self-tolerance. In addition, PD-1 is also known to play a critical role in the suppression of antigen-specific T-cell response in diseases such as cancer and viral infection (Postow et al 2015, Sharpe et al 2007). PD-1 binds to PD-L1, which is highly upregulated on many types of tumor cells as well as immune cells; therefore, targeting PD-L1 is an alternate approach for the treatment of some types of cancer.

In the clinical setting, therapeutic use of blocking antibodies to either PD-L1 or PD-1 has been validated as an effective cancer treatment. Durable clinical responses in a wide variety of solid and hematologic malignancies has led to marketing approvals of the anti-PD-1 antibodies pembrolizumab, cemiplimab, and nivolumab, as well as the anti-PD-L1 antibodies atezolizumab, durvalumab, and avelumab.

2.2. Study Rationale

2.2.1. Scientific Rationale for Study Design

This open-label, nonrandomized study will evaluate the efficacy and safety of INCB086550, a first-in-class oral inhibitor of PD-L1, as initial immune checkpoint inhibitor therapy in participants with select solid tumors (ie, HCC, melanoma, NSCLC, RCC, and urothelial carcinoma) in which the efficacy of PD-(L)1 inhibitors has previously been established. INCB086550 selectively binds to PD-L1 with high affinity, thereby inhibiting the interaction of PD-L1 with PD-1. INCB086550 also reduces surface PD-L1 expression by inducing PD-L1 dimerization and subsequent internalization. Treatment with INCB086550 results in immune activation as evidenced in preclinical and/or clinical studies by increased nuclear factor of activated T cells activity and cytokine production. The primary endpoint of this study is ORR assessed by RECIST v1.1 as determined by the investigator. Secondary [REDACTED] endpoints include safety and tolerability, [REDACTED] changes observed with INCB086550 treatment.

2.2.2. Justification for Dose

INCB086550 will be administered orally in 21-day or 28-day cycles at a dose of 400 mg BID or lower.

The dose was selected based on clinical and safety data from the Phase 1 first in human dose escalation trial (INCB 86550-102). As of 30 OCT 2020, INCB086550 has been evaluated in

48 participants with advanced cancer in the Phase 1 study. Participants have been treated at 100 mg QD (n = 6), 200 mg QD (n = 3), 200 mg BID (n = 10), 400 mg QD (n = 4), 400 mg BID (n = 18), 800 mg QD (n = 1), and 800 mg BID (n = 6). INCB086550 has been generally well-tolerated, and no dose-limiting toxicities have been observed to date. The most frequently occurring TEAEs regardless of causality were decreased appetite (22.9%), fatigue (22.9%), nausea (22.9%), increased blood creatinine (20.8%), constipation (18.8%), diarrhea (18.8%), and increased lipase (16.7%). The most frequently occurring TEAEs assessed as related to INCB086550 by the investigator were nausea (16.7% each) and increased lipase (10.4%). Most TEAEs were Grade 1 or 2 in severity. Serious TEAEs occurred in 16 participants (33.3%). Serious TEAEs that occurred in more than 1 participant were asthenia (n = 2, 4.2%), immune-related peripheral neuropathy (n = 2, 4.2%), and pneumonia (n = 2, 4.2%). Serious TEAEs with a fatal outcome were dyspnea, intracranial hemorrhage, and cerebrovascular accident, each in 1 participant (2.1%). All serious TEAEs with a fatal outcome were assessed as not related to INCB086550 by the investigator. Refer to the INCB086550 [IB](#) for more detailed information.

Immune activation has been observed in participants who received doses of INCB086550 at 200 mg QD and higher. Participants whose drug exposure correlated with $\geq 80\%$ inhibition of PD-L1 in an ex vivo whole blood assay had increases in immune markers of T-cell activation or exhaustion (Ki-67, PD-1, ICOS, and/or TIM3) and interferon-related cytokines in plasma (CXCL9, CXCL10, IFN γ). These findings align with those seen with anti-PD-(L)1 monoclonal antibodies.

As of 01 MAR 2021, 6 participants in Study INCB 86550-102 have had investigator-assessed objective responses per RECIST v1.1. The following responses have been observed: confirmed CR in a participant with squamous cell anal carcinoma (400 mg BID), unconfirmed PR in a participant with squamous cell anal carcinoma (800 mg BID), confirmed PR in a participant with MSI-H colorectal carcinoma (400 mg BID), confirmed PR in a participant with ovarian cancer (400 mg BID), unconfirmed PR in a participant with MSI-H colorectal carcinoma with neuroendocrine histology (400 mg BID), and confirmed PR in a participant with MSI-H colorectal carcinoma (400 mg BID).

The short half-life of INCB086550 ($t_{1/2} = 8.62$ hours) facilitates the investigation of alternative study dosing schedules to optimize benefit/risk. Therefore, intermittent and/or step-down dosing schedules of INCB086550 may be investigated in specified cohorts. These alternative schedules will consist of INCB086550 administered at or below 400 mg BID daily, followed by a period of either no treatment (intermittent dosing) or lower dosing (step-down dosing). These cycles will then be repeated.

2.3.1. INCB086550 Preclinical Background

[figure not shown]
INCB086550 binds to, and reduces the cellular surface expression of PD-L1 with high affinity. For example, PD-L1 expression was decreased following treatment with INCB086550 in MDA-MB-231 breast cancer cells (which express high levels of PD-L1) with an IC_{50} of 2 nM. Similarly, INCB086550 reduced PD-L1 expression on IFN γ -stimulated human peripheral blood monocytes with an IC_{50} value of 12.2 nM (see Figure 2).

Figure 2: INCB086550 Reduces Tumor PD-L1 Expression

INCB086550 also appears as efficacious as atezolizumab in preclinical humanized mouse model studies. Figure 3 shows that INCB086550 and atezolizumab produce a similar reduction of tumor volume in humanized mice bearing MDA-MB-231 tumors.

Figure 3: MDA-MB-231 Humanized Mouse Model

More detailed information about the preclinical activity of INCB086550 may be found in the [IB](#).

2.3.2. INCB086550 Nonclinical Safety Summary

In vitro studies were conducted to characterize the potential risks of inhibiting the PD-(L)1 interaction with INCB086550. These studies demonstrated that INCB086550 binds to human PD-L1 and disrupts the PD-L1/PD-1 interaction at nanomolar concentrations. Clinical studies with blocking antibodies to either PD-1 or PD-L1 have shown an induction of autoimmune responses. Given the mechanism of action of INCB086550, autoimmune AEs may be seen upon administration. Nonclinical pharmacology and toxicology studies have shown no adverse effects or target organ toxicity.

In the pivotal 28-day studies, INCB086550 was well tolerated at all tested doses up to 1000 mg/kg in rats and 715 mg/kg per day in monkeys. Findings associated with INCB086550 in rats were observed only at 1000 mg/kg per day and included decreased red blood cell mass (red blood cells, hemoglobin, and hematocrit), higher reticulocyte counts and red cell distribution, higher neutrophil and monocyte counts, and histiocytic infiltrates in the duodenum, jejunum, and/or ileum, and increased apoptosis/necrosis in the ileum in both males and females. The severity of these findings was limited to minimal to mild, and they were thus considered nonadverse. Treatment-related findings in monkeys were limited to emesis at doses \geq 200 mg/kg per day with no evidence of target organ toxicity.

Consistent with pharmacodynamic data, INCB086550 reduced the growth of MDA-MB-231 in humanized NSG mice and increased the number of CD4 T cells after 28 days of treatment. INCB086550 induced statistically significant TGI compared to vehicle control. The dose levels of INCB086550 0.2, 2, and 20 mg/kg induced TGI of 40%, 49%, and 52%, respectively. A similar study was conducted using immunocompromised Balb/C nu/nu mice as the host, and no TGI was found. These results indicate that an intact immune system is required for the efficacy of INCB086550. Similar data were obtained using MC38 tumor cells that genetically overexpressed human PD-L1. INCB086550 induced statistically significant TGI compared with the vehicle control. The dose levels of INCB086550 2, 20, and 200 mg/kg induced TGI of 37%, 60%, and 71%, respectively. Consistent with the MDA-MB-231 xenograft data, INCB086550 did not inhibit MC38-hPD-L1 tumor growth in immunocompromised NSG mice. This indicates that an intact immune system is required for the efficacy of INCB086550. Dose-dependent tumor growth inhibition and PD-L1 reduction were observed. Accordingly, increasing numbers

of infiltrating CD8 T cells were observed after INCB086550 administration. Antitumor activity was abolished in immunocompromised animals for both preclinical mouse models, suggesting an immune-mediated mode of action.

More detailed information about the known and expected benefits and risks and reasonably expected AEs of INCB086550 may be found in the [IB](#).

3. OBJECTIVES AND ENDPOINTS

[Table 7](#) presents the objectives and endpoints.

Table 7: Objectives and Endpoints

Objectives	Endpoints
Primary	
To determine the ORR of participants treated with INCB086550.	ORR, defined as the percentage of participants with a best overall response of CR or PR confirmed by at least 1 repeat assessment \geq 28 days later according to RECIST v1.1 as determined by the investigator.
Secondary	
To determine the efficacy of INCB086550 in participants with advanced solid tumors in respect to DCR.	DCR, defined as the percentage of participants with a best overall response of CR or PR confirmed by at least 1 repeat assessment \geq 28 days later, or SD for \geq 12 weeks, by investigator assessment per RECIST v1.1.
To determine the efficacy of INCB086550 in participants with advanced solid tumors in respect to DOR.	DOR, defined as the time from the earliest date of CR or PR confirmed by at least 1 repeat assessment \geq 28 days later until the earliest date of disease progression by investigator assessment per RECIST v1.1, or death due to any cause, if occurring sooner than progression.
To evaluate the safety of INCB086550 in participants with advanced solid tumors.	Safety is determined by monitoring the frequency and severity of AEs, including the evaluation of laboratory tests, vital signs, and ECGs
[REDACTED]	

4. STUDY DESIGN

4.1. Overall Design

This study is a Phase 2, open-label, global, multicenter study designed to assess the clinical activity and safety of INCB086550 as initial immune checkpoint inhibitor therapy in participants with advanced selected solid tumors in which the efficacy of PD-(L)1 inhibitors has previously been established. Participants will be enrolled at 1 or more dose levels into disease-specific cohorts as indicated in [Figure 1](#) and Section [5.1](#), with a safety/efficacy run-in analysis in up to 15 participants and a nonbinding interim futility analysis planned after approximately 50% of the participants in each cohort are evaluable for response using the RECIST evaluable population.

The primary endpoint is confirmed ORR as determined by the investigator using RECIST v1.1.

The study consists of 3 periods: screening, study drug treatment, and follow-up.

Eligible participants in a given dose level will receive INCB086550 either in continuous, intermittent, or step-down treatment schedules at or below 400 mg BID daily. For participants on BID treatment, study drug will be administered orally in the morning and evening, approximately 12 hours apart. For participants on QD treatment, study drug will be administered orally in the morning. Treatment cycles may be 28 days (see [Table 3](#) and [Table 4](#)) or 21 days (see [Table 5](#) and [Table 6](#)), and this will be specified for each dose level.

Treatment may be delayed for up to 28 days to allow for resolution of toxicity. The treating investigator should contact the medical monitor to discuss the case of any participant whose treatment has been interrupted for more than 28 days before restarting treatment with INCB086550. See Section [6](#) for additional details.

A maximum study treatment duration of 2 years is allowed. Participants who achieve a CR may discontinue INCB086550 after 4 additional cycles (with a minimum of 1 year of treatment) upon consultation with the medical monitor.

The follow-up period will begin once a participant has completed 2 years of study treatment or has met criteria for discontinuation from study drug. Participants will be evaluated for AEs (including irAEs) for 90 days after the last dose of study drug.

Once participants discontinue treatment, they will enter the follow-up period [REDACTED]. [REDACTED]. Participants who discontinue study treatment without experiencing disease progression will enter the follow-up period and continue to undergo tumor assessments according to the SoA (see [Table 3](#), [Table 4](#), [Table 5](#), and [Table 6](#)) until they experience disease progression, the start of a new anticancer treatment, withdrawal of consent, lost to follow-up, the end of the study, or death.

[REDACTED] The analytes to be evaluated in the safety laboratory analyses are found in [Table 17](#).

4.2. Overall Study Duration

The study begins when the first participant signs the ICF. The end of the study is defined as the date of the last visit of the last participant in the study. Participants completing treatment or prematurely discontinuing the study drug will be followed [REDACTED]

A participant is considered to have completed the study if he/she has completed all periods of the study [REDACTED]

4.3. Study Termination

The investigator retains the right to terminate study participation at any time, according to the terms specified in the study contract. The investigator is to notify the IRB/IEC in writing of the study's completion or early termination, send a copy of the notification to the sponsor or sponsor's designee, and retain 1 copy for the site study regulatory file.

The sponsor may terminate the study electively, if, for example, required by regulatory decision or upon advice of the DMC. If the study is terminated prematurely, the sponsor will notify the investigators, the IRBs and IECs, and regulatory bodies of the decision and reason for termination of the study. The DMC will recommend termination of the study if warranted, as described in Section 5.6.

5. STUDY POPULATION

Deviations from eligibility criteria are not allowed because they can potentially jeopardize the scientific integrity of the study, regulatory acceptability, and/or participant safety. Therefore, adherence to the criteria as specified in the Protocol is essential. Prospective approval of Protocol deviations to recruitment and enrollment criteria, also known as Protocol waivers or exemptions, are not permitted.

5.1. Inclusion Criteria

Participants are eligible to be included in the study only if all of the following criteria apply:

1. Ability to comprehend and willingness to sign a written ICF for the study.
2. Men and women 18 years of age or older.
3. Measurable disease per RECIST v1.1.
4. ECOG performance status of 0 to 1 for all tumor types. Urothelial carcinoma allows ECOG of 0 to 2.
5. Histologically or cytologically confirmed disease-specific diagnosis as follows:
 - a. Treatment-naïve, stage IV NSCLC (AJCC v8) in participants whose tumors express PD-L1 TPS \geq 50% using the Dako PD-L1 IHC 22C3 assay and who have no known activating genomic aberrations that require targeted therapy (eg, EGFR, ALK, ROS, BRAF).

- b. Locally advanced, and unresectable or metastatic UC of the renal pelvis, ureter, bladder, or urethra (including transitional cell and mixed transitional or nontransitional cell histologies) in participants who are cisplatin-ineligible, who are immune checkpoint inhibitor-naïve, and whose tumors express high PD-L1 (CPS ≥ 10) using the Dako PD-L1 IHC 22C3 assay.
Exception for UC: Previous systemic therapy for locally advanced and unresectable or metastatic UC is not allowed except for neoadjuvant or adjuvant chemotherapy if more than 12 months before disease recurrence.
- c. Advanced HCC that is not amenable to curative surgery or local treatment in participants who have received at least 1 previous line of systemic therapy (ie, sorafenib or lenvatinib) or who were intolerant of sorafenib/lenvatinib treatment, have a Child-Pugh score of ≤ 6 (Child-Pugh A), and who are immune checkpoint inhibitor-naïve. Participants with HBV infection are required to be receiving effective antiviral therapy and have a viral load < 100 IU/mL at screening; participants with HCV must have no detectable HCV RNA after curative therapy. Participants with fibrolamellar and mixed hepatocellular/cholangiocarcinoma subtypes are not eligible.
Exception for HCC: Participants without access to prior systemic therapy (ie, sorafenib or lenvatinib).
- d. Advanced or metastatic RCC with a clear cell component with or without sarcomatoid features in participants who have received prior systemic therapy for their disease (up to 2 previous regimens of a VEGF or mTOR inhibitor) and who are immune checkpoint inhibitor-naïve.
Exception for RCC: Participants without access to prior systemic therapy (ie, VEGF or mTOR inhibitors).
- e. Unresectable stage III or IV melanoma (excluding ocular/uveal melanoma) in participants who are immune checkpoint inhibitor-naïve. BRAF V600 mutation status must be known.
Exception for melanoma: Participants may have received 1 prior line of therapy. This therapy could include previous treatment with BRAF/MEK inhibitors in participants with known BRAF V600 mutation or chemotherapy.

6. Willingness to avoid pregnancy or fathering children based on the criteria below ([CTFG 2020](#)).

- a. Men must agree to take appropriate precautions to avoid fathering children (with at least 99% certainty) from screening through 190 days after the last dose of study drug (or longer as appropriate based on country-specific requirements) and must refrain from donating sperm during this period. Permitted methods that are at least 99% effective in preventing pregnancy (see [Appendix A](#)) should be communicated to the participants and their understanding confirmed.

b. Women of childbearing potential must:

- have a negative serum pregnancy test at screening and must agree to take appropriate precautions to avoid pregnancy (with at least 99% certainty) from screening through 190 days after the last dose of study treatment. Additionally, monthly telephone visits should take place to check pregnancy status (which may include home pregnancy tests) during the period when contraception is mandatory (190 days after the last dose of study drug). Permitted methods that are at least 99% effective in preventing pregnancy (see [Appendix A](#)) should be communicated to the participants and their understanding confirmed.
- refrain from donating oocytes from 30 days before the first dose of study drug until 190 days after the last dose.

c. Women of nonchildbearing potential (as defined in [Appendix A](#)) are eligible.

7. Participants must have radiologic documentation of disease progression after treatment with available therapies except for participants with NSCLC, who are required to be treatment-naïve.

5.2. Exclusion Criteria

Participants are excluded from the study if any of the following criteria apply:

1. Prior receipt of an anti-PD-1, anti-PD-L1, or anti-PD-L2 agent, or treatment with an immune modulator (eg, CTLA-4, GITR, LAG3, TIM3, OX40, ICOS, IL2, 4-1BB, CAR-T).
2. Receipt of any anticancer therapy or participation in another interventional clinical study.
Note: For RCC and HCC, the participant must not have received treatment within 21 days or 5 half-lives (whichever is longer) before the first administration of study drug.
3. Radiotherapy within 14 days of first dose of study treatment (28 days for pelvic radiotherapy or 6 months for thoracic region radiotherapy that is > 30 Gy).
4. Concomitant treatment with moderate and potent CYP3A4/CYP3A5 inhibitors or inducers (see [Appendix E](#)).
Note: A washout period \geq 5 half-lives before the first dose of INCB086550 is required for enrollment into the study for prior treatment with CYP3A4/CYP3A5 inhibitors/inducers.
5. Toxicity of prior therapy that has not recovered to \leq Grade 1 or baseline (with the exception of anemia not requiring transfusion support and any grade of alopecia). Endocrinopathy, if well-managed, is not exclusionary and should be discussed with the medical monitor.
6. Participant has not recovered adequately from toxicities and/or complications from surgical intervention before starting study drug.
7. Participants with laboratory values at screening defined in [Table 8](#).

Table 8: Exclusionary Laboratory Values

Laboratory Parameter		Exclusion Criterion
Hematology		
a	Platelets	$\leq 100 \times 10^9/L$
b	Hemoglobin	$\leq 9 \text{ g/dL}$ or $< 5.6 \text{ mmol/L}$ (transfusion is acceptable to meet this criterion)
c	ANC	$\leq 1.5 \times 10^9/L$
Hepatic		
d	ALT	$> 2.5 \times$ institutional ULN For participants with HCC or liver metastases: $> 5 \times$ ULN
e	AST	$> 2.5 \times$ institutional ULN For participants with HCC or liver metastases: $> 5 \times$ ULN
f	Total bilirubin	$\geq 1.5 \times$ institutional ULN unless conjugated bilirubin \leq ULN (conjugated bilirubin only needs to be tested if total bilirubin exceeds ULN). If there is no institutional ULN, then direct bilirubin must be $< 40\%$ of total bilirubin.
g	Alkaline phosphatase	$\geq 2.5 \times$ ULN. Note: Participants with 1) bone metastases and 2) no hepatic parenchymal metastases on screening radiographic examinations may enroll if the alkaline phosphatase is $< 5 \times$ ULN. Participants with 1) bone metastases and 2) hepatic parenchymal metastases on screening radiographic examinations may enroll if the alkaline phosphatase is $< 5 \times$ ULN only with medical monitor approval.
Renal		
h	Serum creatinine; or calculated CrCl ^a	Serum creatinine $> 1.5 \times$ institutional ULN; or CrCl $< 50 \text{ mL/min}$ for participants with creatinine levels $< 1.5 \times$ institutional ULN. For participants with UC or RCC, CrCl $< 40 \text{ mL/min}$ with creatinine levels $< 1.5 \times$ institutional ULN.
Coagulation		
i	INR or PT	$> 1.5 \times$ institutional ULN for participants not receiving anticoagulant therapy. For participants with HCC: $> 2.3 \times$ institutional ULN.
j	aPTT or PTT	$> 1.5 \times$ institutional ULN for participants not receiving anticoagulant therapy
k	Albumin	$< 3 \text{ g/dL}$ For participants with HCC or liver metastases: $< 2.5 \text{ g/dL}$

^a The Cockcroft and Gault equation (1976): CrCl = $\{([140-\text{age}] \times \text{weight in kg}) / (72 \times \text{serum creatinine})\} \times 0.85$ (if female).

8. Active malignancy of a type not included in the study population requiring treatment.

Note: Exceptions include basal cell carcinoma of the skin, squamous cell carcinoma of the skin that has undergone potentially curative therapy, in situ cervical cancer, or early-stage endometrial cancer.

9. Active autoimmune disease requiring systemic immunosuppression in excess of physiologic maintenance doses of corticosteroids ($> 10 \text{ mg of prednisone or equivalent}$).

10. Evidence of interstitial lung disease or active, noninfectious pneumonitis.

11. Untreated or known active CNS metastases and/or carcinomatous meningitis.

Note: Participants with previously treated brain metastases may participate provided they are stable (without evidence of progression by imaging for at least 28 days before the first dose of study drug and any neurologic symptoms have returned to baseline), have no evidence of new or enlarging brain metastases or CNS edema, and have not required steroids for at least 7 days before the first dose of study drug.

12. With the exception of participants with HCC, known active HAV, HBV, or HCV infection, as defined by elevated transaminases with the following serology: positivity for HAV IgM antibody, anti-HCV, anti-HBc IgG or IgM, or HBsAg (in the absence of prior immunization).

Note: For participants with cleared prior HBV infection: HBV prophylaxis should be considered per investigator discretion. Monitor for HBV reactivation every 3 cycles by performing HBV viral load and HBsAg serology test. Additional viral serologic testing may be performed at the investigator's discretion.

Note: Participants with no prior history of HBV infection who have been vaccinated against HBV and who have a positive antibody against HBsAg as the only evidence of prior exposure may participate in the study.

Note: Hepatitis C antibody-positive participants who received and completed treatment for hepatitis C that was intended to eradicate the virus may participate if HCV RNA levels are undetectable.

13. Active infection requiring systemic therapy.

14. Receipt of systemic antibiotics within 28 days of first dose of study treatment.

15. Probiotic usage during screening and throughout the study treatment period.

16. Participants who are known to be HIV-positive.

17. Participants with impaired cardiac function or clinically significant cardiac disease:

- a. New York Heart Association Class III or IV cardiac disease, including preexisting clinically significant ventricular arrhythmia, congestive heart failure, or cardiomyopathy.
- b. Unstable angina pectoris \leq 6 months before study participation.
- c. Acute myocardial infarction \leq 6 months before study participation.
- d. Other clinically significant heart disease (ie, \geq Grade 3 hypertension, history of labile hypertension, or poor compliance with an antihypertensive regimen) must have recovered (to baseline or \leq Grade 1) from toxicity associated with prior treatment.

18. History or presence of an ECG finding that, in the investigator's opinion, is clinically meaningful. Screening QTcF interval $>$ 450 milliseconds is excluded; in the event that a single QTc is $>$ 450 milliseconds, the participant may enroll if the average QTc for the 3 ECGs is \leq 450 milliseconds. For participants with an intraventricular conduction delay (QRS interval $>$ 120 milliseconds), the JTc interval may be used in place of the QTc with sponsor approval. The JTc must be \leq 340 milliseconds if JTc is used in place of the QTc. Participants with left bundle branch block are excluded.

Note: Participants with QTc prolongation due to pacemaker may enroll if the JTc is normal (\leq 340 milliseconds) and medical monitor approval is granted.

19. Female participant is pregnant or breastfeeding within the projected duration of the study, starting with the screening visit through the 90-day safety follow-up, or male participant is expecting to conceive or father children within the projected duration of the study, starting with the screening visit through 100 days after the last dose of study treatment.
20. Has received a live vaccine within 90 days of the planned start of study drug.

Note: Examples of live vaccines include, but are not limited to, the following: measles, mumps, rubella, chicken pox, some zoster, yellow fever, rabies, BCG, and typhoid vaccines. Seasonal influenza vaccines for injection are generally killed virus vaccines and are allowed; however, intranasal influenza vaccines are live-attenuated vaccines and are not allowed.

21. Current use of a prohibited medication as described in Section 6.6.3.
22. Life expectancy $<$ 3 months.
23. Known hypersensitivity or severe reaction to any component of study drug or formulation components.
24. History of organ transplant, including allogeneic stem cell transplantation.
25. Presence of a gastrointestinal condition that may affect drug absorption.
26. Any condition that would, in the investigator's judgment, interfere with full participation in the study, including administration of study drug and attending required study visits; pose a significant risk to the participant; or interfere with interpretation of study data.

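### Outside the HCC cohort, Exclusion Criterion 12 does not exclude an HBsAg-positive participant with normal ALT/AST, and no antiviral rule, HBV-DNA limit or scheduled viral load then applies

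*Protocol*

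**What the plan says.** Criterion 12 in Protocol Section 5.2 applies to every cohort except HCC. It excludes "known active HAV, HBV, or HCV infection, as defined by elevated transaminases with the following serology", followed by a list of markers that includes HBsAg and anti-HCV. Three notes follow:

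- The first concerns past infection: "For participants with cleared prior HBV infection: HBV prophylaxis should be considered per investigator discretion". It continues: "Monitor for HBV reactivation every 3 cycles by performing HBV viral load and HBsAg serology test".
- The second admits vaccinated participants whose only marker is the antibody to HBsAg.
- The third says that treated, antibody-positive HCV participants "may participate if HCV RNA levels are undetectable".

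For HCC, Inclusion Criterion 5c is explicit. "Participants with HBV infection are required to be receiving effective antiviral therapy and have a viral load" below 100 IU/mL at screening, and "participants with HCV must have no detectable HCV RNA after curative therapy". The viral-load row in Tables 3 to 6 runs every 2 cycles from Cycle 3 and is restricted to HCC participants who have viral hepatitis.

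Two general exclusions could also apply. Criterion 13 reads "Active infection requiring systemic therapy". Criterion 26 leaves to the investigator any condition that would "pose a significant risk to the participant; or interfere with interpretation of study data".

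**The concern.** Section 8.3.6.2 gives the purpose of screening serology as ruling out hepatitis. Yet in four of the five cohorts, criterion 12 does not act on a positive HBsAg when ALT/AST is normal. Section 5 bars eligibility waivers and requires the criteria to be followed as written, so the wording decides who enters.

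The first stake is participant safety. Section 2.1 notes that PD-1 helps to suppress antigen-specific T-cell responses in viral infection, and the study drug blocks that pathway. The protocol already treats HBV reactivation as a risk, because it monitors cleared infection.

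The second is the safety data. Table 10 manages raised transaminases as immune hepatitis, with systemic corticosteroids if Grade 2 or short-lived Grade 3 elevations persist after 3 days. SAP Section 9.2.2 picks out potential irAEs from a term list, with later clinical review. Without serial HBV DNA, an unrecognised HBV flare could be treated and counted as an irAE.

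The third is consistency. Two sites could handle the same carrier differently under criteria 13 and 26.

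**Working it through.** No plan figure needs reproducing. The check is to trace participants through the rules.

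**Entry.** Take a non-HCC participant who is HBsAg-positive with ALT and AST in the normal range. Criterion 12 gives no cut-off for elevated, but normal values fail that condition on any reading.

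- Criterion 12: serology condition met, transaminase condition not met, so not excluded.
- Table 8: the ALT and AST limits are 2.5 x ULN (5 x ULN with liver metastases), so not excluded.
- Criterion 13: excluded only if the infection is judged active and to require systemic therapy.
- Criterion 26: excluded only by investigator judgment.

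**After entry.** The mandated HBV provisions compare as follows.

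| Participant | Antiviral therapy | HBV-DNA limit at entry | Planned on-treatment viral load |
|---|---|---|---|
| HCC with HBV (5c, Tables 3 to 6) | Required | < 100 IU/mL | Every 2 cycles from Cycle 3 |
| Non-HCC, cleared HBV (criterion 12, first note) | Considered, at discretion | None | Every 3 cycles, with HBsAg |
| Non-HCC, HBsAg-positive, normal ALT/AST | None stated | None stated | None stated |

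The third row cannot borrow from the second. The first note is for cleared infection and tests HBsAg to detect reactivation, so it describes people who are HBsAg-negative at entry. Current infection therefore gets less mandated protection than past infection.

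**HCV.** The third note implies that RNA-positive participants are not meant to enter, but it addresses those who have completed treatment. No criterion says the same of an untreated non-HCC participant with normal ALT/AST.

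**Screening HBV DNA.** Table 17 lists HBV-DNA and HCV-RNA under serology, and the Serology row is marked at screening for everyone. The separate viral-load row has its own screening mark, for HCC only. Whether non-HCC participants have a screening HBV DNA is therefore unclear. If they do, no limit is attached to it.

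**Size of the group under the rule** (Protocol Table 20, per dose level):

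- Non-HCC: 32 (NSCLC) + 25 (UC) + 23 (RCC) + 30 (melanoma) = 110.
- All cohorts: 110 + 42 (HCC) = 152.
- Share: 110/152 = 72.4% under criterion 12; 42/152 = 27.6% under 5c.
- If every cohort were filled at two dose levels: 220 of 304.

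The number who would be HBsAg-positive with normal ALT/AST cannot be derived, because the documents give no carrier frequency.

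**The case against.** The strongest reply is that the protocol has more cover than criterion 12 alone suggests:

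- Chemistry is drawn at least on Day 1 of each cycle, and in Schedules A and B also on Day 15 of Cycles 2 to 6. Section 8.3.6 asks for results to be reviewed and acceptable before a new cycle starts.
- Table 10 acts from Grade 1, with repeat laboratory tests once or twice a week. At Grade 2 drug is withheld and tests are repeated every 3 days.
- Section 6.5.1 tells the investigator to look for other causes of each AE, viral infection included.
- Sections 8.3.6 and 8.3.6.2 allow extra tests when clinically indicated, and a DMC reviews safety.
- Appendix D lists active viral hepatitis as an alternative cause, once potential Hy's law criteria are met.
- Criterion 13 can be read to exclude carriers who need antivirals. That narrows the gap to those whose infection is not judged to need treatment.

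All of this stands. A reader might otherwise infer that carriers enter with no safeguard at all, and the documents do not support that. But the laboratory and AE steps start after ALT/AST rises or an event appears, and criteria 13 and 26 depend on judgment. Criterion 13 could also remove a treated, suppressed carrier while admitting an untreated one with normal ALT.

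It can also be argued that positive serology was meant to exclude by itself, given Section 8.3.6.2 and the permissive second and third notes. That may be the intent. If so, the operative definition does not deliver it.

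**Conclusion.** The gap is real. As written, criterion 12 does not exclude an HBsAg-positive non-HCC participant with normal ALT/AST, and no other provision gives that participant an entry rule or a planned viral load. It is best treated as a wording gap with a safety consequence, partly covered elsewhere. It has no bearing on the ORR design or the sample size.

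Two stronger readings should be avoided. First, 110 of 152 is the number subject to the criterion and not the number affected, which could be zero or a few. The 220 of 304 further assumes that every cohort runs at two dose levels, whereas Section 2.2.2 speaks of alternative schedules in specified cohorts. All of these are planned numbers, and SAP Section 11.2.1 reports early termination with minimal enrollment, so the practical value now lies mainly in any reuse of the criterion. Second, the HCV gap is smaller than the HBV gap, because the third note already shows the intent. It does not justify excluding on anti-HCV alone.

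The conclusion rests on the ordinary reading of the criterion, in which both conditions are required, and on an HBsAg-positive person not counting as cleared.

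**What to change.** For non-HCC participants, amend as follows:

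1. **HBV entry.** Make HBsAg positivity exclusionary whatever the transaminases, unless the participant is on effective antiviral therapy with screening HBV DNA below a limit confirmed by the sponsor's clinicians (for example the < 100 IU/mL of 5c). State that HBV suppressed in this way does not by itself meet criterion 13. Leave the anti-HBc wording and its note unchanged.
2. **HBV monitoring.** Extend the every-3-cycle viral load in the criterion 12 note to any HBsAg-positive participant admitted. Give it its own footnote in Tables 3 to 6, separate from the HCC row that runs every 2 cycles.
3. **HCV entry.** Exclude detectable HCV RNA whatever the transaminases. Do not make anti-HCV positivity alone exclusionary.
4. **Screening tests.** Require HBV DNA or HCV RNA at screening only in serology-positive participants. This also settles the conflict between Table 17 and the HCC-only row.

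The cost is amendment wording and nucleic acid tests in a small subset. HBsAg, HBV-DNA and HCV-RNA are already listed in Table 17, so no new type of test is introduced. The downside is that a few carriers become ineligible or need antivirals and periodic viral loads. If the sponsor means to admit untreated carriers, the protocol should say so and schedule their monitoring.
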